Interventions for resolving PIUO are time and resource intensive. They require a focused approach to assessing all the underlying possibilities for the PIUO and addressing each potential source of pain one at a time. Tackling PIUO requires systematic, comprehensive, process-oriented thinking applied by an interdisciplinary team with flexibility in terms of approach and time. There have been recommendations in the literature about how to approach the problem of PIUO in children with SNI, but these recommendations have never been subjected to systemic evaluation as complex interventions, for example by following an integrated clinical pathway.^{12,37} Integrated clinical pathways (also called "care pathways" or "critical pathways") are structured, sequenced approaches guiding the delivery of healthcare, often with a multidisciplinary perspective.³⁸ They provide algorithms to be followed in the assessment and treatment of conditions, but are not intended to be rigidly followed; instead, integrated clinical pathways delineate a foundation for a clinician's approach to a complex problem, thereby avoiding inefficiencies in evaluation or resource use. Integrated clinical pathways are a form of Complex Interventions and have been developed for sickle cell pain,³⁹ childhood asthma,⁴⁰ appendicitis,⁴¹ autoimmune conditions,⁴² inborn errors of metabolism,⁴³ and cerebrospinal fluid shunt management.⁴⁴ Despite their complexity, integrated clinical pathways are appropriate interventions for evaluation by Randomized Controlled Trial (RCT).⁴⁵ RCTs of integrated clinical pathways have been proposed and/or completed for complex, multi-factorial patient problems including lung disease, heart failure, gastrointestinal surgery, stroke, and hip fractures.^{38,46-48}

In this study, we will use a waitlist-controlled RCT design, with 120 children randomized to PIUO Pathway or waitlist (standard care) treatment arms. This design was chosen strategically, with consideration of both the special pediatric population being studied and the ethical inappropriateness of randomly assigning children to a placebo group when pain is the target condition.

The Study Sequence, Events Grid and a detailed depiction of the PIUO Pathway are shown in Appendix 1, 1a and 1b.

STUDY SITES

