Exclusion criteria: Children will be excluded if they are not within the specified age range; have the communication capabilities and cognitive development to localize their pain or have an explained and treatable cause of pain and irritability.

Randomization

Participants will be randomized to start the PIUO Pathway or to the waitlist control arm. The list of random allocations will be generated at WCHRI's DCC centre using REDCap. An automated audit trail of all transactions, including assigned study identification number, treatment allocation, and time and date of the transaction will be recorded by REDCap. Randomization will be stratified by site and using permuted blocks of sizes 2 and 4.

Sample Size

The sample size calculation was based on the anticipated treatment difference between PIUO Pathway arm and waitlist control arm in the period between 8 and 12 weeks. As stipulated in the section on primary outcomes (page 12) a patient will be considered a success if they are judged to be in the lowest two pain categories (A or B) on consecutive visits beginning at weeks 8 or 10. We anticipate that a 25% response to treatment during this period would be the minimal required to be viewed as clinically important, and we believe that a 25% response rate is achievable. The response rate during this period in the waitlist control is assumed to be zero, although we have set it at 5% to be cautious. To achieve 80% power using a two-tailed $\alpha=0.05$ using the Fisher's exact conditional test for comparing proportion, we require 57 patients per group. The Site Leads confirm that this number is readily obtainable within the proposed timeline.

Recruitment Procedures

It is anticipated that the same recruitment procedures will be followed at all four sites. However, minor modifications may be necessary for compliance with the individual ethics board at those institutions. Recruitment will be amongst outpatients, however if a child is hospitalized after enrolment, s/he can remain on the study.

Families will be made aware of the study via the following two channels:

1. A letter (Appendix 7) will be sent on behalf of the Principal Investigator, by the Site Leads to respective community pediatricians and sub-specialty clinics where children with SNI often receive care (e.g., Neurology, Complex Care, Orthopaedics, etc.). The letter invites them to refer patients to the study.

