- The Pain Survey tool will measure pain and irritability persistence and distress level throughout the study. A quick, two question assessment, the pain survey is taken from the Washington group Extended Question Set on Functioning (WGES-F) and is adapted here for use in children. The pain question set has been shown to have good validity and is able to correlate with other pain measurements in adults.⁵⁰ Although this two-question pain survey is simple, it is sufficiently informative so as to be of use in describing a child's pain, without unduly burdening parents with an overload of questions every two weeks. Pain Surveys will be completed biweekly throughout the Study as described below. Participants will be deemed to have had a positive outcome if they score in category A or B (see Appendix 5) on two consecutive visits. We will compare those who have a positive response on weeks 8, 10 and 12 between intervention and waitlist group.
- PROMIS-57 (Patient Reported Outcomes Measures Information System) is a multi-dimensional tool that will assess parents' well-being in the face of their child's chronic pain and irritability. This assessment is one of the two primary outcome of this project. PROMIS-57 was developed as part of an initiative of the US Department of Health and Human Services to establish a common set of patient reported outcome measures (www.healthmeasure.net). The PROMIS tools are found to be valid and reliable. There is a Canadian PROMIS coordinator as well, and support is available for translation and adaption to the REDCap database which we will be using. There are several PROMIS tools assessing various elements of adult and child health and well-being. The PROMIS-57 tool assesses across the following domains: physical function, anxiety, depression, fatigue, sleep, social participation, and pain interference in daily activity. While we cannot attribute all changes in quality of life to improvement in the child's pain and irritability, we will analyze to look for high degrees of correlation.

ANALYSIS

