The primary analytic strategy is based on the assumption that it will take some time after the screening period (weeks 0-2), the onset of randomization (week 2-3) and the Pathway initiation (weeks 4-10 in the Pathway group) for the intervention to have its full impact. As well, to determine the impact relative to the Waitlist group, the comparison must take place before the intervention is delivered to the Waitlist group (i.e. prior to cross-over). Thus, the primary analysis will focus on the measurements taken at weeks 8, 10, and 12.

The primary outcome is a change in Pain Survey score, moving a child from any high pain and irritability score (C, D, and E), to a low score (A, B) for 2 continuous reporting periods. A level B score ("little pain" on "some days") is clinically acceptable in this health challenged popula-

tion, although not ideal. Previous work has indicated that complete absence of pain is not always achievable in this population.^{3, 33}

The primary comparison will use a Fisher's exact test to compare the proportion of patients achieving a successful outcome in the period starting between week 10 and 12. We will also perform an adjusted analysis using logistic regression and treating the baseline category as a covariate.

In addition, we will compare the Pathway groups on each domain of the PROMIS-57 instrument at week 10. The dependent measures will be the domain scores at week 10, the covariates will be the scores at baseline of each domain, and the independent variable will be the Pathway group. Multiple linear regression will be used to evaluate the intervention differences. In the primary analysis, all participants measured on week 10 will be included. Multiple imputation will be used in a sensitivity analysis to include participants without measures on week 10.

As a secondary analysis, we will determine whether the intervention had an effect in the Waitlist group by comparing their measurements on the pain outcomes at week 14, 16 and 18 with their week 10 measurements (just before they cross over to the Pathway).

DATA STORAGE

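### PROMIS-57 is called a primary outcome and tested on seven domains, but the protocol does not say what decides it, and its other sections treat the Pain Survey as the only primary outcome

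*Protocol*

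**What the plan says.** Under DATA COLLECTION TOOLS, Primary Outcomes, the protocol says of PROMIS-57: "This assessment is one of the two primary outcome of this project". It describes the instrument as a measure of parents' well-being with seven domains: "physical function, anxiety, depression, fatigue, sleep, social participation, and pain interference in daily activity".

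The ANALYSIS section says "we will compare the Pathway groups on each domain of the PROMIS-57 instrument at week 10". Each week-10 domain score is regressed on group and the baseline score of that domain. Participants measured at week 10 are analysed, and multiple imputation is a sensitivity analysis. The paragraph gives no significance level, lead domain, summary score or adjustment, and no pattern of results that would count as an effect.

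Two other places give a different status:

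- **STUDY AIMS, Objectives** names one primary outcome, the reduction in the child's pain and irritability scores. It places improved family quality of life among the secondary outcomes.
- **ANALYSIS** defines the primary outcome, in the singular, as a change in Pain Survey category. It brings in PROMIS-57 afterwards as an additional comparison.

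The only stated test level is in Sample Size, for the Pain Survey: "To achieve 80% power using a two-tailed $\alpha=0.05$ using the Fisher's exact conditional test for comparing proportion, we require 57 patients per group".

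**The concern.** For the Pain Survey the protocol says what success is: a move from category C, D or E to A or B, held for two consecutive reporting periods. For the other outcome it calls primary, it gives seven parallel comparisons and no rule for reading them. What decides a primary outcome is part of defining that outcome, so this is more than a computing detail.

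One nominally significant domain out of seven is weak evidence of better parent well-being. Nothing in the protocol says whether such a result would count as success on a primary outcome. The conflict over status makes this worse, because the sections support two different answers to how much error control is needed.

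**Working it through.** **1. The plan's own figure.** The only stated design figure is 57 per group for the Pain Survey, from "We anticipate that a 25% response to treatment during this period would be the minimal required to be viewed as clinically important" and a waitlist rate of which the protocol says "although we have set it at 5% to be cautious". Exact enumeration of two-sided Fisher power at 25% versus 5% gives 82.0% at 57 per group and first reaches 80% at 55 (80.1%). The stated 57 is therefore adequate for the Pain Survey. It has no bearing on PROMIS-57, for which the protocol gives no error rate or power.

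**2. Inputs for PROMIS-57.**

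- Number of tests: 7 (Primary Outcomes, list of domains; ANALYSIS, one regression per domain).
- Level per test: two-sided 0.05. This is an assumption, carried over from the Fisher test in Sample Size.
- Correlation between the seven test statistics: not given. A common value ρ from 0 to 0.9 is assumed.

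**3. Independent tests, no true effect.**

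- Any false significant difference: 1 − 0.95^7 = 1 − 0.698 = 30.2%.
- Any false improvement (favourable 2.5% tail only): 1 − 0.975^7 = 1 − 0.838 = 16.2%.

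**4. Correlated tests.** Orient each domain so that a positive statistic favours the Pathway. With c = 1.960 and Z standard normal:

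- Either direction: 1 − E[{Φ((c − √ρ·Z)/√(1−ρ)) − Φ((−c − √ρ·Z)/√(1−ρ))}^7]
- Favourable direction: 1 − E[Φ((c − √ρ·Z)/√(1−ρ))^7]

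Numerical integration over Z gives:

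| Assumed ρ | At least one false difference, either direction | At least one false improvement |
|---|---|---|
| 0 | 30.2% | 16.2% |
| 0.3 | 27.2% | 13.7% |
| 0.5 | 23.0% | 11.5% |
| 0.7 | 17.8% | 8.9% |
| 0.8 | 14.9% | 7.4% |
| 0.9 | 11.4% | 5.7% |
| Single test | 5% | 2.5% |

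For ρ between 0.7 and 0, the chance of a false improvement is 8.9/2.5 = 3.6 to 16.2/2.5 = 6.5 times that of one test.

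**5. Effect of adjusting.** The first Holm step uses 0.05/7 = 0.00714. Seven independent tests at that level give 1 − (1 − 0.00714)^7 = 4.9%, and the error cannot exceed 5% under any correlation.

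**6. Cost of adjusting.** The two-sided critical value at 0.00714 is 2.690. An effect in one domain with 80% power at 0.05 has an expected statistic of 1.960 + 0.842 = 2.802. Its power at the first Holm step is Φ(2.802 − 2.690) = Φ(0.112), or about 54%.

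**The case against.** The strongest reply is that adjustment across domain scores is commonly left to a statistical analysis plan, and that plan is not at hand. The regression itself is stated clearly and contains no error. This stands in part. A reader might infer that the trial has no error control for PROMIS-57, but that can be said only of the protocol. The reply does not reach the conflict between the protocol's own sections, or the use of primary status without saying what decides the outcome.

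Three other stronger readings are tempting, and the documents do not support them:

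- **That 18% to 30% is the risk of a false improvement.** Those figures count differences in either direction. The favourable-direction figures are about 9% to 16%, and the right comparator is 2.5%, not 5%.
- **That the plan accepts any single domain at 5% as proof of benefit.** No section says so. The protocol is silent on the rule and on the level for these tests, and it cautions that not all changes in quality of life can be attributed to the child's pain.
- **That adjustment is needed whatever status PROMIS-57 has.** If it is secondary, as the Objectives and ANALYSIS sections read, adjusting within one supportive instrument is a matter of preference.

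It is also true that parents who know their arm report on themselves. That is a question of bias, which no multiplicity adjustment would address.

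**Conclusion.** The point holds in a limited form. The protocol gives PROMIS-57 primary status in one section, does not treat it as primary in two others, and tests seven domains without saying which domain or combination decides the outcome.

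The sizes in the working rest on two assumptions that the protocol does not supply: 0.05 per domain and a common correlation. Even at the highest correlation examined, 0.9, both error rates remain more than twice those of a single test. How much this matters depends on the status chosen. It is a real weakness if PROMIS-57 is primary, and mainly a matter of labelling if it is secondary. The reading that family quality of life in the Objectives means PROMIS-57 is an inference, but no other listed data collection tool measures it.

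**What to change.** Reconcile the Primary Outcomes section with Objectives and ANALYSIS by choosing one of two options.

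**Option A: Pain Survey as sole primary outcome.** Remove the primary label from PROMIS-57 and add to ANALYSIS: *The Pain Survey outcome is the sole primary outcome. The seven PROMIS-57 domain comparisons are secondary. They will be reported as estimates with 95% confidence intervals and will support no confirmatory claim.* The only cost is the confirmatory claim on parent well-being.

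**Option B: PROMIS-57 stays primary.** Correct Objectives and the singular wording in ANALYSIS, and add: *The seven domain p-values will be adjusted by Holm's method to hold the family-wise error at 5%. An effect on parent well-being will be claimed only for domains significant after adjustment. Unadjusted estimates with 95% confidence intervals will be reported for all domains.* The cost is power: an effect confined to one domain with 80% power at 0.05 has about 54% at the first Holm step. This controls error within PROMIS-57 only. The text should also say how the two primary outcomes are read together, since two independent claims at 5% each carry 1 − 0.95^2 = 9.75%.

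Either option takes a few sentences and needs no new data or patients.

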In addition to reviewing all previous work up related to pain and irritability, we will establish a baseline for participants' expectations to the effectiveness of the PIUO Pathway. Pain is highly modifiable by psychological factors such as beliefs and expectations, which may influence treatment response (via placebo analgesia). This is especially important in this context of children with SNI where caregivers play a key role in assessment and management of pain and a placebo-by-proxy effect might occur based on the parents' perceptions/behavior.⁴⁹ To evaluate the Impact of Expectations all families will be asked at the outset and at the end of the Pathway if they expect that participation will be of benefit to them and/or their child and if they found the Pathway beneficial.

After the baseline has been established, children will then be randomly assigned to (1) PIUO Pathway arm with immediate intervention or (2) waitlist control arm. Data will be collected on pain and irritability and health during the waitlist period for control subjects in the same way as for those on the immediate intervention arm.

Children assigned to the immediate PIUO Pathway arm will start with Step 1 right after randomization. The waitlist control arm will be ten weeks in duration and then children will cross over to Step 1 of the PIUO Pathway. For participants on either arm, starting at enrolment, the Study Research Nurse will administer a Pain Survey and provide a consultation (Appendix 5 and 5b) every two weeks by phone. The Research Nurse can be contacted by the family for consultation

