at any time during the study (standard working hours) in between the scheduled bi-weekly phone call. The Pain Survey tool measures pain and irritability persistence and distress level through a composite score of two questions asking parents to report on their child's experience and behavior within the last two weeks. The tool is taken from the Washington Group Extended Question Set on Functioning (WGES- F) developed by a United Nations commission on disability statistics and is intended to capture a measure of physical impairment along with questions on pain, fatigue and depression. The extended set of questions has been adopted by the United Nations as a scale to measure disability at an epidemiological level and the two-question pain set has been shown to demonstrate validity in an adult population.⁵⁰ These two questions on pain ("how much pain did you have" and "how bad is the pain") have been adapted for use with children and are included in the study as markers of pain persistence and distress.

The RN Consultation has a two-fold objective: 1) To gather clinical information to assist the study team in assessing and treating the child's PIUO and 2) to provide the parent with a consultation in regards to any measurements they might take or have taken to relieve their child's PIUO. The clinical information relevant in this regard includes any changes in health, medications or interventions outside the study (including care provided by community physicians, therapists, and alternative medicine practitioners) that might impact PIUO.

Once on the PIUO Pathway (regardless of starting arm) children will receive the intervention for a minimum of 10 weeks. Children will stay on the Pathway until the condition improves/resolves or until all investigations and interventions within the PIUO Pathway have been exhausted without improvement or resolution to the condition or after 6 months have passed, whichever comes first. There will be a follow-up assessment 2 months after the child completes the PIUO Pathway either with or without resolution or improvement.

Efficiency of the PIUO Pathway will be measured by tracking time needed, and number of investigations required, for those patients who turn out to have an identifiable cause for pain and irritability. Parents will be given a chance to provide feedback on the study and their participation via a survey, answering questions detailed in the Family Feedback Form (Appendix 11)

STUDY PROCEDURES

The PIUO Pathway

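### The ANALYSIS section gives two incompatible cross-over times for waitlist controls: after the week 12 survey for the primary comparison, but just after week 10 for the secondary one

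*Protocol*

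**What the plan says.** All references are to the protocol.

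- **ANALYSIS, first paragraph.** The reason for the primary window is that "the comparison must take place before the intervention is delivered to the Waitlist group (i.e. prior to cross-over"). From this it concludes: "Thus, the primary analysis will focus on the measurements taken at weeks 8, 10, and 12". Week 12 must therefore be untreated time in controls.
- **ANALYSIS, same paragraph.** The calendar has screening in weeks 0-2, followed by "the onset of randomization (week 2-3) and the Pathway initiation (weeks 4-10 in the Pathway group").
- **ANALYSIS, last paragraph.** The secondary analysis compares the waitlist group's pain outcomes "at week 14, 16 and 18 with their week 10 measurements (just before they cross over to the Pathway").
- **STUDY SEQUENCE.** "The waitlist control arm will be ten weeks in duration and then children will cross over to Step 1 of the PIUO Pathway". The ten weeks are not tied to the numbered study weeks. For the other arm, "Children assigned to the immediate PIUO Pathway arm will start with Step 1 right after randomization".
- **STUDY SEQUENCE.** Pain Surveys are taken every two weeks from enrolment and ask about the child's "experience and behavior within the last two weeks".
- **Objectives and Sample Size.** Success means the two lowest pain categories on two consecutive visits, the first at week 8 or week 10.
- **ANALYSIS, Fisher's test sentence.** The proportions compared are of patients "achieving a successful outcome in the period starting between week 10 and 12".

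**The concern.** In a waitlist trial the cross-over date decides which control measurements are untreated. Here one section gives two dates. Its primary paragraph needs week 12 to fall before cross-over. Its secondary paragraph puts cross-over directly after week 10, although a week 12 survey exists because surveys are biweekly.

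Two things are at stake. If controls cross over after week 10, the last primary survey is partly or wholly a measurement on the Pathway. If they cross over at week 12-13, the secondary analysis uses a reference that is not the last untreated one, and its follow-up surveys come sooner after cross-over than the text implies. With four sites, each could schedule Step 1 for controls differently and still be following some sentence of the protocol.

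**Working it through.** **The plan's own figure.** Sample Size gives 57 per group for 25% versus 5%, two-sided Fisher's exact test, alpha 0.05, 80% power. Exact enumeration gives 80.1% at 55 per group (79.1% at 54) and 82.0% at 57. The figure is sound, and the cross-over date does not enter it.

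**Step 1: date the cross-over.** Cross-over week = week in which the waitlist starts + 10.

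- Waitlist starts at randomization, week 2-3: 2 + 10 = 12 and 3 + 10 = 13, so week 12-13.
- Waitlist starts at week 0: 0 + 10 = 10, which matches the secondary paragraph. On the ANALYSIS calendar, however, the arm would then last only 10 - 2 = 8 or 10 - 3 = 7 weeks after randomization, not ten.
- Numbering the weeks from randomization also gives week 10, but that conflicts with a calendar that puts randomization at week 2-3.

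**Step 2: apply each date to the surveys.** The qualifying pairs under Objectives and Sample Size are 8-10 and 10-12.

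| | Cross-over at week 12-13 | Cross-over just after week 10 |
|---|---|---|
| Control time on Pathway at weeks 8 / 10 / 12 | 0 / 0 / 0 | 0 / 0 / up to 12 - 10 = 2 weeks |
| Primary pairs with treated control time | 0 of 2 | 1 of 2 (10-12) |
| Last untreated survey | week 12 | week 10 |
| Week 10 reference precedes cross-over by | 12 - 10 = 2 to 13 - 10 = 3 weeks | about 0 |
| Weeks 14 / 16 / 18, time since cross-over | 1-2 / 3-4 / 5-6 weeks | about 4 / 6 / 8 weeks |

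The first column satisfies the primary paragraph and fails the secondary one; the second column does the reverse. With cross-over at week 13, the week 14 survey recalls weeks 12 to 14, so 1 of its 2 weeks is still waitlist time.

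**Step 3: who is affected if cross-over follows week 10.** A control in category A or B at both week 8 and week 10 is already a success. A control outside A/B at week 10 cannot succeed on either pair. Only a control in A/B at week 10 but not at week 8 can have the result decided by the week 12 survey. If the Pathway works, this adds control successes and shrinks the difference. If it has no effect, nothing changes, so type I error is not inflated.

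**Step 4: the Fisher's test sentence.** Read literally, pairs starting at week 10 or 12 are 10-12 and 12-14. The 8-10 pair drops out and both remaining pairs contain week 12. Week 14 is after cross-over on either date (14 - 13 = 1 and 14 - 12 = 2 weeks, or 14 - 10 = 4 weeks). This conflicts with Sample Size, where pairs start at week 8 or 10.

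**The case against.** The strongest reply is that the intended date is recoverable. STUDY SEQUENCE gives the order: baseline, then random assignment, then a ten-week waitlist arm. A child cannot be in that arm before allocation, so with randomization at week 2-3 cross-over is at week 12-13. Primary Outcomes also places week 12 in the between-arm comparison, and the secondary analysis skips week 12 as a post-cross-over survey, which fits its being control time (though a wash-in would explain that too). On this view the primary endpoint is untouched, week 10 is still an untreated reference, and the defect is a loose parenthesis in one uncontrolled secondary analysis.

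Most of this stands, and week 12-13 is adopted here as the better reading. It does not remove the inconsistency, because on that date week 10 is not just before cross-over. Nor does it stop a site from acting on the secondary paragraph. Appendix 1, 1a and 1b are not shown and may indicate the intended date, but no date makes both statements true.

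It is also fair to say that the 12-14 pair is a strained reading, since Primary Outcomes and the first ANALYSIS paragraph stop at week 12. The conflict over where pairs start is a related but separate wording fault and adds no weight here. The contrast between starting Step 1 directly after randomization and Pathway initiation over weeks 4-10 may only reflect a roll-out phase.

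**Conclusion.** The point holds as an internal inconsistency of minor to moderate weight. On the better reading (cross-over at week 12-13) the primary window is clean, and the fault is a secondary reference taken 2-3 weeks before cross-over when the week 12 survey is available. If sites follow the secondary paragraph, the 10-12 pair includes up to 2 weeks of Pathway time in controls, contrary to the plan's own rule. That bias is toward no difference and probably small: it needs the response pattern in Step 3, control success is planned at no more than 5% (about 3 of 57), and Step 1 opens with history, examination and directed testing.

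A reader might infer that the primary comparison is contaminated and power is lost. The documents do not support this. They give no rate for controls who would succeed only through early Pathway time, so any power figure rests on an assumption. One assumed extra success on top of 5% (5% + 1/57 = 6.75%) gives 70% power at 57 per group, but the 5% is already a cautious allowance over an expected zero. Starting from zero, one success (1/57 = 1.75%) gives 97%. Neither figure carries the verdict. PROMIS-57 at week 10 is untreated in controls on either date.

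**What to change.** Amend the protocol wording as follows.

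1. State that week 0 is enrolment and that the ten-week waitlist runs from randomization.
2. State that no control starts Step 1 before the week 12 Pain Survey is complete. On the calendar this is 12 - 3 = 9 to 12 - 2 = 10 weeks after randomization.
3. State in ANALYSIS, including the Fisher's test sentence, that primary pairs start at week 8 or week 10 only.
4. Make week 12 the pre-cross-over reference for the within-waitlist analysis.
5. Record each child's Step 1 date, and describe the week 14, 16 and 18 surveys by time since actual cross-over. Moving them later would be a preference; the inconsistency does not require it.
6. Align the two descriptions of when the immediate arm starts the Pathway.

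The cost is wording and one date field. No patients or surveys are added, because Pain Surveys are already biweekly. If cross-over at week 10 was intended, controls wait about 2-3 weeks longer in pain, which the investigators should weigh openly.
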